Overview: The proposed design is a mixed methods, interventional study with concurrent controls to examine the effects of an intervention to improve role concordance on decisional outcomes among newly diagnosed breast cancer patients. Providers will be blind to the patient's preferred decision making role in the first half of the study and then informed of the preferred role in the second half of the study. The intervention will be a short conversation that providers will have with patients at the beginning of the clinic visit where the provider identifies the patient's preferred role and their desire to help the patient achieve it. Quantitative comparisons before and after implementation of the intervention and qualitative analyses of the recorded clinical encounters will be performed to evaluate the effects of the provider directed behavioral intervention to improve role concordance. This study design was chosen because once the intervention is introduced providers may have difficulty omitting this behavior from the clinical encounter and this could confound our results. If patient-level randomization was used, providers would need much more oversight and coaching in order to not "forget" which patient is in which arm and the study effects may be biased toward the null. In this small study, if provider-level randomization was used, this could significantly bias assessments of patient involvement due to inherent differences in how the providers approach clinical interactions at baseline. Also, we do not anticipate substantial variability in the pre and post populations during the short time period of the study other than the date of their consultation and, thus, we expect that the populations will be very similar in other characteristics. We plan to examine differences between pre and post-intervention patients to evaluate this.

Objectives:

1. Investigate the impact of a brief provider-led intervention about the patients' preferred role in treatment decision making on role concordance. **We hypothesize that:**
 - a. Role concordance will be improved when the preferred role is discussed with the patient at the beginning of the encounter.
 - b. The provider's perception of the role achieved will be more concordant with the patient's perception when the preferred role is discussed.

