Methodology: The Patient Preference Scale is the initial scale used in the study and identifies 5 different roles in decision making (Fig. 1). Following completion of the consent process, participants will be asked just prior to the first clinic visit with the surgeon to identify their most preferred role for treatment decision making during that encounter. This will be designated as the preferred role for evaluation of role concordance. For the first 50 patients, the providers will be blinded to the preferred role. After the clinic visit, the participants will complete the Patient Perception Scale which measures patients' perception of the achieved role in the treatment decision making process. After the clinic visit, providers will also complete the Provider Perception Scale which measures the provider's perception of the role achieved by the patient. These three scales are shown in Table 1. The Patient Perception Scale and the Provider Perception Scale will be compared to evaluate the degree of patient-provider concordance between achieved roles. Analysis will also be performed to establish the proportion of patients with perfect role concordance between their preferred and achieved roles. The degree of discordance can also be measured by comparing the number of roles between the preferred role and the achieved role on the 5-point Likert-type scales

Table 1.

Patient Preference Scale (prior to clinic visit)	Patient Perception Scale (after clinic visit)	Provider Perception Scale (after clinic visit)
I prefer to make the final selection about which treatment I will receive	I made the final decision about which treatment I would receive.	The patient made the final decision about which treatment she would receive.
I prefer to make the final selection of my treatment after seriously considering my doctor's opinion.	I made the final selection of my treatment after seriously considering my doctor's opinion	The patient made the final decision about which treatment she would receive after seriously considering my opinion.
I prefer that my doctor and I share responsibility for deciding which treatment is best for me.	My doctor and I shared responsibility for deciding which treatment was best	I shared responsibility with the patient for making the final decision about

	for me.	treatment she would receive.

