The primary aim of our study (a) is to evaluate patient perception of whether the patient achieved his/her preferred role in the treatment decision. This aim will be met by estimating perception concordance between baseline and after the clinic visit within the intervention and control groups, and testing for group differences in concordance. A secondary goal (b) will be to similarly estimate concordance of provider's perception of the patient's preferred role versus the patient's perception of the achieved role (where both scales will be measured after the clinic visit). In addition, we also plan to test the following outcomes between groups: c) patient's satisfaction with the decision making process, d) FACT-B assessment of short-term QOL, e) decision regret, f) OPTION assessment of patient involvement and g) completion or intention to complete therapies. Finally, we will compare the patient role concordance estimated in a) with improved short-term and longer-term improvements in: outcomes c)-g). Specific methods corresponding to each analysis objective are described below.

a-b) Concordance measures. The patient and provider perception scales consist of 5 levels ranging from active to passive involvement in treatment decisions. Consistent with other similar studies [5-7], our primary concordance measure will be defined as exact agreement in patient responses between the baseline and post clinic visit. Within each group we will provide concordance rates and the associated 95% confidence interval (CI) using the Wilson Score interval approach. We will also report the weighted Kappa coefficient and its 95% CI. Group differences in concordance will be tested using a chi-squared or Fisher's exact test. As a sensitivity analysis for this assessment, we may adjust for potential confounders in a logistic framework predicting concordance. We will consider the following variables for adjustment if they are associated with the concordance outcome: age, education level, and stage of disease.

c) Patient's satisfaction with the decision making process. Satisfaction with the decision making process will be measured directly after the clinic encounter using a modified version of the Holmes-Rovner Satisfaction with

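### Neither the primary concordance test nor its optional sensitivity model protects against a difference between the two phases in the mix of preferred roles, although preferred role is half of the outcome and is recorded on every patient beforehand

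*Combined protocol and SAP*

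**What the plan says.** Under Statistical Analysis, a-b), "our primary concordance measure will be defined as exact agreement in patient responses between the baseline and post clinic visit". The baseline response is the preferred role: under Methodology, patients "identify their most preferred role for treatment decision making during that encounter" before they see the surgeon, in both halves of the study.

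The opening of Statistical Analysis assigns the first 50 patients to control and the next 50 to the intervention. Recruitment expects 50 in each of two years.

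For the comparison, "Group differences in concordance will be tested using a chi-squared or Fisher's exact test". Adjustment is optional: "As a sensitivity analysis for this assessment, we may adjust for potential confounders in a logistic framework predicting concordance". The candidates are "age, education level, and stage of disease", each considered only if associated with concordance. The longer list in c), to which d), f) and g) refer back, adds treatment variables only. Preferred role is on neither list. Elsewhere, role preference is analysed only in relation to the type of surgery.

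Two related provisions exist. The Overview plans to look for differences between pre- and post-intervention patients, but names no variables and no consequence. Section a-b) reports a weighted kappa within each group.

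**The concern.** Concordance means that the achieved role equals the preferred role, so it is likely to depend on which role was preferred. Suppose, as an extreme case, that the achieved role ignored preference altogether. Concordance among patients preferring a given role would then equal the frequency with which that role is achieved. It would be the same for all five roles only if each were achieved 20% of the time.

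Randomisation does not balance the preference mix here, because the groups are consecutive. If the later group holds more patients whose preference is easily met, concordance rises without any intervention effect. If it holds fewer, a real effect is hidden. At stake are the primary comparison and the effect estimate that the plan wants to carry into a larger grant application.

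Preferred role is measured before the intervention, so adjusting for it is legitimate.

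**Working it through.** **The plan's own figure.** Inputs from Sample Size Justification: 50 per group, 50% concordance in control, a 28-point increase (to 78%), two-sided Fisher test at 0.05, stated power 80%. Exact enumeration over two binomial distributions gives 78.9%, which agrees to within about a point. The uncorrected chi-squared test gives 84.3%.

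**Size of the possible bias.** With no intervention effect:

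spurious difference = (shift between phases in the share holding a preference) × (gap in concordance between preference groups)

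The documents give neither factor, so both are assumed. Average concordance is kept at the plan's 50%. For a gap of 65% versus 35% (30 points), with rejection rates by exact enumeration:

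| Shift in mix | Spurious difference | Chi-squared rejects | Fisher rejects |
|---|---|---|---|
| 0 | 0 | 5.7% | 3.5% |
| 10 points | 0.10 × 0.30 = 3.0 points | 6.8% | 4.3% |
| 15 points | 0.15 × 0.30 = 4.5 points | 8.2% | 5.4% |
| 20 points | 0.20 × 0.30 = 6.0 points | 10.2% | 6.9% |

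Over a wider assumed range (shifts of 10 to 30 points, gaps of 20 to 40 points), the spurious difference runs from 2 to 12 points. If the shift works against the intervention, Fisher power for a true 28 points falls from 78.9% to 67.5% at 3 points of bias and 54.9% at 6 points.

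**Does stratifying remove it?** In simulation with the 30-point gap and a 20-point shift, the crude chi-squared test rejected 9.9% of the time with a mean bias of 5.9 points. A Mantel-Haenszel test stratified on preference rejected 4.6% with bias near zero. With equal mixes and a true 28-point effect, stratification raised power from about 84–85% to about 88%.

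**Three levels or five?** Agreement is scored on five levels, so collapsing can hide a shift. Assume 25% and 65% concordance for the two roles in which the patient decides, and a 15-point shift between those two. Crude rejection was then 10.6%, three-level Mantel-Haenszel 9.4% and five-level 5.3%. Five levels cost no power relative to three.

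**Chance imbalance.** For a preference held by 20% to 50% of patients, the phases differ by 10 points or more in 26% to 37% of trials by chance alone, and by 20 points or more in 2% to 6%. With no systematic shift the crude chi-squared test still rejected 5.7%, the same as its baseline.

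**Room in a logistic model.** Expected discordant patients: 50 × 0.50 + 50 × 0.22 = 36. Group plus four role indicators gives 36/5 = 7.2 per predictor. Adding age, education and stage at one term each gives 36/8 = 4.5, just below the 5 to 10 that the plan states for g).

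**The case against.** The covariate list serves only an optional sensitivity analysis. A reader might infer that leaving preferred role off it biases the primary comparison. It does not: the primary test is unadjusted, and a longer list would leave that test unchanged. This objection stands. What remains is that neither the test nor its only planned safeguard addresses this variable.

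A reader might also treat chance imbalance as inflating the error rate. It does not, because the nominal error rate already covers it. Only a systematic shift does that, and the Overview expects similar populations over a short study. That expectation is plausible but is not a safeguard, particularly with enrolment planned over two years.

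The Overview's remark about "inherent differences in how the providers approach clinical interactions at baseline" might be read as saying that patients who match a surgeon's default style are concordant without help. It concerns differences between providers and is given as a reason against provider-level randomisation. Differing styles among the four surgeons could even narrow a pooled gap by role.

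The illustrated bias is small beside the 28-point target, and under Fisher's test, on which power is based, rejection stays near nominal at shifts of 10 to 15 points. That is correct and limits the severity.

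Finally, the pre/post check and the weighted kappa both bear on the issue. The first names neither preferred role nor an action. The second allows for the role distributions within each group, but the between-group test is on raw agreement. Neither replaces an adjusted comparison.

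**Conclusion.** The gap is real and its size is moderate and uncertain. The documents establish that preferred role is half of the outcome, is known before the visit for every patient, and is adjusted for nowhere, while the groups are consecutive. They do not establish bias, which needs both a systematic shift in mix and concordance that differs by role.

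On the assumed 65%/35% contrast, a 10 to 15 point shift would add or remove 3.0 to 4.5 points. That matters more for the estimate carried forward to a larger study than for the test itself.

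For Objective 2, where concordant and discordant patients are compared on satisfaction, quality of life and regret, a reader might infer that the results are confounded by preferred role. Nothing in the documents shows that preference independently affects those outcomes. It is a plausible confounder and no more.

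**What to change.** In a-b), pre-specify as a definite analysis a concordance comparison stratified by or adjusted for baseline preferred role, for example Mantel-Haenszel. It should not depend on whether role tests as associated with the outcome. Use the five levels, collapsing only where they are sparse, and report the result beside the unadjusted test. Tabulate preferred role by phase, and concordance by preferred role within phase.

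In c) to f), add preferred role to the candidate covariates for the concordant-versus-discordant comparisons. In g), add it only if the plan's 5 to 10 events per predictor allows.

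The cost is SAP wording and no new data. The analysis uses up to four degrees of freedom and leaves less room for age, education and stage in the logistic model. A stratum with patients from only one phase contributes nothing to a Mantel-Haenszel comparison, which is the reason to allow collapsing. Stratifying on role addresses only this source of difference between phases, not other changes over time.

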Intervention: The intervention will take place in the second half of the study, where the research assistant will inform the provider of the patient's preferred role based on the Patient Preference Scale prior to the clinic visit. The provider will then have a brief conversation at the beginning of the clinic visit where they state "I see that you prefer to have treatment decisions made (*together, by yourself, by me*) today. I appreciate knowing this information." The rest of the encounter will proceed as per the provider's usual practice. All other study procedures will be the same and the same perception scales will be used after the clinic visit and concordance and discordance will be examined as described in the study flow diagram.

Outcomes: The primary outcomes will be role concordance and patient satisfaction with the decision process. Secondary outcomes will be role perception concordance between provider and patient, quality of life at 2 to 6 weeks and 6 months after initial clinic visit, decision regret at 2 to 6 weeks and 6 months after initial clinic visit, and completion or planned completion of recommended therapies at 6 months. These time points were chosen to provide an early assessment of the impact of the intervention and to see if the results are durable after a longer period of time while still allowing us to conclude the study within the funding timeframe. There is evidence that decision regret is stable over time out to 4 years after diagnosis [4]. We will also correlate role

preference and concordance with surgical procedure performed or planned to look for associations between these measures and type of surgery received or planned, controlling for ineligibility for breast conservation.

Risks and Benefits of Participation: Participation is completely voluntary and may be withdrawn at any time. This is a low risk study, but some patients may experience distress from the questions on the surveys. If a patient experiences distress, she will be referred to our in-clinic Licensed Care Social Worker and she will make appropriate referrals to psychiatric care if necessary. There is also a low risk of loss of privacy and patients will be made aware of this. The benefits of participation are greater patient awareness of their own preferences and decisions.

Please see the study flow diagram on the following page.

Record decisions made and intentions
to complete therapy

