Decision scale which combines several elements of decisional satisfaction and is designed to measure satisfaction with the decision regardless of prognosis or outcome [5, 8]. It also correlates with decision confidence. It uses a Likert-type ranking of 6 items related to the decision. The modified version will measure the satisfaction with the process of decision making rather than the decision itself. Group satisfaction differences will be assessed using a two-sample two-tailed t-test. We will also use linear regression to consider adjusting for the potential confounders described above (a-b) along with the following treatment related variables: type of surgery received and the sequencing of treatment (chemo first vs. surgery first), surgical complications, recommendation for chemotherapy, and recommendation for radiation treatment in these analyses. We will also compare satisfaction with concordance within groups using t-tests (or regression to adjust for covariates). Finally, we will test whether the relationship between satisfaction and concordance differs across groups using linear regression and testing for significance of a group*concordance interaction.

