f) OPTION assessment of patient involvement. The outcome of patient involvement at the clinic encounter will be measured using the OPTION scale. This scale was developed to measure the extent to which providers involve patients in decisions. A description of the measures used and timeline is illustrated in Table 2. With this scale, 2 independent raters will use a 12 item list to code and score a clinical consultation. It provides a reliable method for detecting differences between the extent of patient involvement with good inter-rater reliability and inter-rater agreement [10, 11]. Raters will be hired graduate students who will be trained in this method, with each rater coding and scoring the first 10 transcripts followed by comparison of the results using the intraclass correlation coefficient (ICC) and its 95% CI before switching to a single rater per transcript method. These scores will be compared between the intervention and control groups for differences in patient involvement using a two-sample t-test and linear regression to adjust for the covariates described in c). We will also compare patient involvement with concordance within groups using t-tests (or regression to adjust for covariates). Finally, we will test whether the relationship between involvement and concordance differs across groups using linear regression and testing for significance of a group*concordance interaction.

g) *Completion or intention to complete therapies.* Group differences in completion or intention to complete recommended therapies will be assessed at 6 months after the clinic visit through chart review of all participants' charts. Intent will be defined as initiation or scheduled initiation of a recommended treatment. The variables of decision made (i.e. type of surgery or sequence of therapy) and completion or intention to complete recommended therapies will be compared between groups using a chi-squared or Fisher's exact test. We will also use a logistic regression framework to test whether the relationship between concordance with completion differs by group. We will consider adjusting for a few covariates described in c), keeping in mind a minimum of 5-10 events per predictor in our models. [12]

Table 2.

Measure Name	Assesses	Prior to Clinic Visit	Immediately After Clinic Visit	2 to 6 Weeks After Clinic Visit	6 Months After Clinic Visit
Patient Preference Scale	Patient's preferred role in decision making process	X			

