Patient Perception Scale	Role the patient perceives they played in decision making process		X		
Provider Perception Scale	Role the provider perceives the patient played in the decision making process		X		
FACT-B	Breast cancer specific health related quality of life	X		X	X
Decision Process Satisfaction Scale	Level of satisfaction patient had with the decision making process		X		
Decision Regret Scale	Regret about decision made			X	X
OPTION Scale	3rd party assessment of patient involvement in decision making (from recorded encounter)		X		

Sample Size Justification

Concordance estimates. A similar study conducted by Bilodeau and Degner estimated 50% agreement between a patient's initial decision-role preference and the role that was achieved [13]. Within each group (n=50), we expect to achieve a confidence interval (CI) width of 29% for an expected concordance of 50%, corresponding to a 95% CI of 36%-64%.

Comparison of intervention versus control concordance. With 50 subjects per group we would have 80% power to detect an absolute increase in concordance of 28% in the intervention versus the control group using a two-sided Fisher's exact test at a 0.05 significance level.

Selected References

1. Hack, T.F., et al., *Behind closed doors: systematic analysis of breast cancer consultation communication and predictors of satisfaction with communication.* Psychooncology, 2010. **19**(6): p. 626-36.
2. Clayton, M.F., et al., *Assessing patient-centered communication in a family practice setting: how do we measure it, and whose opinion matters?* Patient Educ Couns, 2011. **84**(3): p. 294-302.
3. Hack, T.F., et al., *Promoting consultation recording practice in oncology: identification of critical implementation factors and determination of patient benefit.* Psychooncology, 2013. **22**(6): p. 1273-82.
4. Martinez, K.A., et al., *Decision Regret following Treatment for Localized Breast Cancer: Is Regret Stable Over Time?* Med Decis Making, 2015. **35**(4): p. 446-57.
5. Lantz, P.M., et al., *Satisfaction with surgery outcomes and the decision process in a population-based sample of women with breast cancer.* Health Serv Res, 2005. **40**(3): p. 745-67.
6. Janz, N.K., et al., *Patient-physician concordance: preferences, perceptions, and factors influencing the breast cancer surgical decision.* J Clin Oncol, 2004. **22**(15): p. 3091-8.

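### Satisfaction and OPTION are fixed on the visit day, yet sections c) and f) list surgery received and surgical complications, which come later, as adjustment variables (minor)

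*Combined protocol and SAP*

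**What the plan says.** **Satisfaction.** Under Statistical Analysis, c): "Satisfaction with the decision making process will be measured directly after the clinic encounter using a modified version" of a published scale. Table 2 marks it only in the column for immediately after the visit. The group comparison is a two-sample t-test, and then: "We will also use linear regression to consider adjusting for the potential confounders described above (a-b) along with the following treatment related variables". Those variables are "type of surgery received and the sequencing of treatment (chemo first vs. surgery first), surgical complications", followed by the recommendations for chemotherapy and for radiation.

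**OPTION.** Under f), scores are compared between groups "using a two-sample t-test and linear regression to adjust for the covariates described in c"). Table 2 describes OPTION as a "3rd party assessment of patient involvement in decision making (from recorded encounter").

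**Standing of the two outcomes.** The Outcomes section states: "The primary outcomes will be role concordance and patient satisfaction with the decision process". The Statistical Analysis puts the weight elsewhere: "The primary aim of our study (a) is to evaluate patient perception of whether the patient achieved" the preferred role. Satisfaction and OPTION follow under "In addition, we also plan to test the following outcomes between groups".

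**Timing of surgery.** Participants are newly diagnosed, previous breast cancer is an exclusion (Study Subjects), and the visit is the first with the surgeon (Methodology). Decisions ultimately made are read from the chart at 6 months (Methodology). Section g) compares surgery type and treatment sequence between groups.

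**The concern.** An adjustment variable is useful in a comparison of two sequential, non-randomised groups when it precedes the outcome and may explain part of the difference. Surgery received and surgical complications do not precede satisfaction or OPTION. They cannot be confounders of either.

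Surgery type may instead be a consequence: of the conversation that opens the visit, of how the visit went, or of both. Section g) tests it as a possible result of the intervention. If it depends on the outcome, or on group while also being linked to the outcome, a regression that holds it constant no longer estimates the group effect. A real difference can shrink, or one can appear where none exists. The groups are the first 50 and the next 50 patients, so a reader will look to the adjusted estimate as the check on confounding. It should not carry this problem.

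The plan is more careful elsewhere: for role concordance, which also concerns the visit, a-b) names only age, education and stage.

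**Working it through.** **1. Order of events, from the text.** Preferred role is recorded; the visit takes place and is recorded; satisfaction is reported; surgery follows; complications follow surgery; the chart is reviewed at 6 months. OPTION is coded later, but what it measures is fixed at the visit. No sentence restricts the list in c) to later outcomes.

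**2. Figures in the plan.** None bears on this point: no SD, effect size or association is given for satisfaction or OPTION. The only power figure concerns concordance (50% against 78%, 50 per group, Fisher's exact test). Exact enumeration gives 78.9% against the stated 80%. Everything below is therefore assumed.

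**3. Set-up.** S is the outcome in SD units, G the group (0/1), and M a later binary surgery choice with P(M=1) = logit⁻¹(a·S + b·(G − 0.5)). The fitted model is S on G and M. With 50 per group the standard error of the unadjusted difference is √(1/50 + 1/50) = 0.20 SD.

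**4. No true effect.** If a = 0 or b = 0 the bias is zero. Otherwise:

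| a | b | M=1, control vs intervention | Bias of adjusted effect | False-positive rate |
|---|---|---|---|---|
| 0.5 | 0.2 | 47.6% vs 52.4% | -0.02 SD | 5.2% |
| 0.5 | 0.4 | 45.3% vs 54.7% | -0.04 SD | 5.5% |
| 0.5 | 0.8 | 40.7% vs 59.3% | -0.09 SD | 7.5% |
| 1 | 0.2 | 47.9% vs 52.1% | -0.03 SD | 5.3% |
| 1 | 0.4 | 45.9% vs 54.1% | -0.07 SD | 6.4% |
| 1 | 0.8 | 41.8% vs 58.2% | -0.14 SD | 11.1% |

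The outcome–surgery correlation is about 0.23 for a = 0.5 and 0.41 for a = 1. Rates come from 40,000 simulated trials; the unadjusted test stays at 4.9–5.1%. A separate simulation with both links at 1 gives -0.17 SD.

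**5. True effect 0.50 SD.** If surgery depends on the outcome only, the adjusted effect is 0.47 SD (a = 0.5) or 0.41 SD (a = 1), and power is 66% or 61% against 69–70% unadjusted. If group also drives surgery directly and both links are 1, the adjusted effect is 0.25 SD, a loss of 0.50 − 0.25 = 0.25 SD.

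**6. Complications.** Suppose they depend only on surgery type, at 5% vs 20% or 5% vs 40%. Adjusting for them alone biases the null cases in step 4 by at most -0.007 or -0.023 SD. Adding them to a model that already holds surgery type changes nothing.

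**7. Surgery type as a proxy.** Let a pre-visit disease feature differ by 0.4 SD between groups, correlate 0.3 with the outcome, and alone drive surgery choice. Unadjusted bias is 0.4 × 0.3 = 0.12 SD. Adjusting for stage, correlated r with the feature, leaves 0.12 × (1 − r²):

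- r = 0.3: 0.109; adding surgery type leaves 0.059–0.091.
- r = 0.5: 0.090; adding surgery type leaves 0.053–0.077.
- r = 0.7: 0.061; adding surgery type leaves 0.041–0.054.

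Dropping surgery type here costs about 0.01–0.05 SD.

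**8. Proxy and consequence together** (r = 0.5). Stage alone leaves +0.089 SD. Adding surgery type gives +0.001, -0.032, -0.029 or -0.073 SD across four link strengths, smaller in absolute size each time. The ranking is not stable. At r = 0.7 with the strongest links, adding surgery type gives -0.075 against +0.060 for stage alone. With the group imbalance reversed (r = 0.5), stage alone gives -0.088 against -0.101 or -0.057 with surgery type.

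**The case against.** **The numbers do not favour removal.** In step 7, and in the main setting of step 8, the model with surgery type is the less biased one. This stands. A reader might infer that removal is shown to reduce bias; it is not. Step 8 shows that the ranking depends on the direction of an unknown imbalance. What remains is the argument from timing.

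**Little depends on it.** Both outcomes keep an unadjusted t-test, adjustment in c) is only to be considered, the study is meant to supply preliminary data for a larger grant, and the Statistical Analysis lists satisfaction after concordance. All of this stands and sets the weight. A reader might infer from the word primary in Outcomes that a primary result is compromised. The documents do not support that, because the t-test does not use these variables.

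**The list is a shared pool.** Sections d) and g) also draw on it, e) follows d), and f) points back to covariates that c) only considers. Loose drafting is a likely explanation, and the contrast between offering in c) and planning in f) is thin. Still, nothing in the text keeps the two variables out of c) and f).

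**Surgery may be chosen during the visit.** The perception scales ask who made the final treatment decision, and Outcomes speaks of surgery received or planned. Surgery type could then be partly a mediator, which is a different path from the one modelled in steps 4 and 5. That still argues against holding it constant when the total group effect is wanted, because the intervention opens the visit. Complications can only follow surgery.

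**Conclusion.** The point holds on timing: type of surgery received and surgical complications come after satisfaction and OPTION, cannot confound them, and do not belong in the adjusted group comparisons of c) and f). Severity is minor.

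The size cannot be determined from the documents. With no true effect, every assumed case stays below one standard error (0.20 SD), and the bias is zero if the links are absent. A loss above one standard error appeared only with a true effect of 0.50 SD and both links strong. Complications bring almost no bias and no confounding control. Whether removing surgery type lowers the net bias is open.

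Two wider readings are not supported. First, treatment sequencing and the chemotherapy and radiation recommendations stand in the same list, but their timing relative to the visit is not stated, so no bias is claimed for them. Second, the point does not carry over to the unadjusted t-tests, to a-b), or to d), e) and g).

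**What to change.** In the adjusted group comparisons of c) and f), remove type of surgery received and surgical complications. Adjust for variables fixed before the visit: age, education, and stage as known at the visit, all already named in a-b). Ineligibility for breast conservation, which Outcomes already uses as a control, may be added if it is known before the visit. Label any model in c) or f) that includes surgery type as exploratory. No change is required for sequencing or for the chemotherapy and radiation recommendations.

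The cost is SAP wording only, with no new data and no change to the t-tests. The downside is that some disease information carried by surgery type is lost, about 0.01–0.05 SD in the assumed proxy case of step 7.
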